## **ECG evaluations**

A listing will be provided presenting all ECG data in a subject with any abnormal values (based on the PI's interpretation). This listing will be sorted by treatment group, subject and visit/time. If there is any abnormality (marked as abnormal by the PI) of an ECG parameter for a subject, all measurements of this parameter for the subject will be presented in this listing. Abnormalities, based on the PI's interpretation, will be flagged. Clinically notable values will also be flagged in the listing using the following criteria:

ECG Parameter	Clinically Notable Criteria
PR	PR > 200 msec
QRS	QRS complex > 120 msec
QTcF	Males: QTcF > 450 msec Females: QTcF > 460 msec

Baseline will be defined as the last available pre-dose measurement.

Summary statistics (absolute values) will be provided by treatment group and visit/time. Measurements obtained at Screening and EoS will be included in the tabulations for the overall safety population only.

A categorical summary of QT/QTcF interval data based on the number of subjects meeting or exceeding predefined limits in terms of absolute QT/QTcF intervals or changes from baseline, at any time post-baseline, will be presented by treatment group. Specifically, frequency counts and percentages will be provided for each category of interest. The QT/QTcF categories of interest will be as follows:

Observed Value (msec)	Change from Baseline (msec)
Males:	
≤ 450	
> 450 - 480	
> 480 - 500	≤ 30
> 500	> 30 - 60
Females:	
≤ 460	> 60
> 460 - 480	
> 480 - 500	
> 500	

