- 12 months of natural (spontaneous) amenorrhea with an appropriate clinical profile (e.g. age appropriate, history of vasomotor symptoms) or
- have had surgical bilateral oophorectomy (with or without hysterectomy) or
- tubal ligation at least six weeks ago.

In the case of oophorectomy alone, only when the reproductive status of the woman has been confirmed by follow up hormone level assessment is she considered not of child bearing potential.

- 20. History of drug abuse or harmful alcohol use within the 12 months prior to dosing, or evidence of such abuse. Harmful alcohol use is defined as a history of, or current alcohol misuse/abuse, defined as "Five or more drinks on the same occasion on each of 5 or more days in the past 30 days."
- 21. Donation of 400 ml or more of blood within 8 weeks prior to baseline, or longer if required by local regulation.
- 22. Inability or unwillingness to undergo repeated venipunctures (e.g., due to poor tolerability or lack of access to veins).
- 23. Any surgical or medical condition which might significantly alter the absorption, distribution, metabolism, or excretion of drugs, or which may jeopardize the subject in case of participation in the study. The investigator should make this determination, at

screening, in consideration of the patient's medical history and/or clinical or laboratory evidence of any of the following:

- Major gastrointestinal tract surgery such as gastrectomy, gastroenterostomy or bowel resection;
- Pancreatic injury or pancreatitis;
- Liver disease or liver injury as indicated by abnormal liver function tests as defined by the following 3 criteria at screening.
 - ALT must be within the normal range;
 - Serum bilirubin must not exceed 1.5 x ULN;
 - GGT, AST and alkaline phosphatase must not exceed 2 x ULN.
- 24. A history of clinically significant ECG abnormalities, or any of the following ECG abnormalities at screening (central read) or baseline (local read):
 - PR > 200 msec
 - QRS complex > 120 msec
 - QTcF > 450 msec (males)
 - QTcF > 460 msec (females)
- 25. Patients with clinically relevant primary sclerosing cholangitis
- 26. Patients who previously received more than one class of biologic therapy for UC (i.e. anti-TNF blockers).
- 27. History or current evidence of colonic dysplasia or adenomatous colonic polyps.

6 Treatment

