8.4.2 Electrocardiogram (ECG)

A central reading of standard 12-Lead ECGs will be implemented. Full details of all procedures relating to the ECG collection and reporting are contained in the core laboratory technical manual or in the Site Operations Manual. At Baseline, local reading is allowed in order to assess the eligibility of the subject before randomization.

PR interval, QRS duration, heart rate, RR interval, QT interval, QTcF (Fridericia QT) will be collected.

The SOM has the preferred sequence of data collection during study visits, notably ECG collection (10 min rest, ECG recording over next 5 min suggested), precedes vital signs and blood sampling.

Clinically significant abnormalities must be reported as adverse events in the AE CRF.

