11.2 Database management and quality control

Novartis staff (or designated CRO working on behalf of Novartis) review the data entered into the CRFs by investigational staff for completeness and accuracy and instruct the site personnel to make any required corrections or additions. Queries are sent to the investigational site using an electronic data query. Designated investigator site staff are required to respond to the query and confirm or correct the data.

Concomitant treatments and prior medications entered into the database will be coded using the World Health Organization (WHO) Drug Reference List, which employs the Anatomical Therapeutic Chemical classification system. Medical history/current medical conditions and adverse events will be coded using the Medical Dictionary for Regulatory Activities (MedDRA) terminology.

Laboratory samples will be processed centrally and the results will be sent electronically to Novartis (or a designated CRO).

ECG readings will be processed centrally and the results will be sent electronically to Novartis (or a designated CRO).

Patient reported outcomes will be collected via paper diaries. Relevant data will be entered into the CRF.

Randomization codes and data about all study drug(s) dispensed to the subject and all dosage changes will be tracked using an Interactive Response Technology (IRT).

Each occurrence of a code break via IRT will be reported to the clinical team and monitor. The code break functionality will remain available until study shut down or upon request of Novartis

The occurrence of relevant protocol deviations will be determined. After these actions have been completed and the database has been declared to be complete and accurate, it will be locked and the treatment codes will be unblinded and made available for data analysis. Any changes to the database after that time can only be made after written agreement by Novartis management.

Commercially Confidential Information

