12.5.1 Safety endpoints

For all safety analyses, the safety set will be used. All tables, figures and listings tables will be presented by treatment group.

Safety summaries (tables, figures) include only data from the on-treatment period with the exception of baseline data which will also be summarized where appropriate (e.g. change from baseline summaries). In addition, a separate summary for death including on treatment and post treatment deaths will be provided, if there were death during the study. In particular, summary tables for adverse events (AEs) will summarize only on-treatment events, with a start date during the on-treatment period (treatment-emergent AEs).

Adverse events

All information obtained on adverse events will be displayed by treatment group and subject.

The number (and percentage) of subjects with treatment emergent adverse events (events started after the first dose of study medication or events present prior to start of double-blind treatment but increased in severity based on preferred term) will be summarized in the following ways:

- by treatment, primary system organ class and preferred term.
- by treatment, primary system organ class, preferred term and maximum severity.
- by treatment, Standardized MedDRA Ouery (SMO) and preferred term.

Separate summaries will be provided for study medication related adverse events, death, serious adverse events, and other significant adverse events leading to discontinuation.

The number and percentage of subjects with adverse events of infections, CCI will be summarized by treatment.

A subject with multiple adverse events within a primary system organ class/preferred term is only counted once towards the total of this primary system organ class/preferred term.

Summaries will also be provided for the number of adverse events by treatment.

Vital signs

Abnormalities (and relevant orthostatic changes) will be flagged and reported. The subjects with abnormal values will be visualized along with all subjects in overlaid individual plots by treatment group.

ECG

Abnormalities will be flagged and reported. For continuous ECG parameters, the subjects with abnormal values will be visualized along with all subjects in overlaid individual plots by treatment group. Clinically notable events such as those in Exclusion Criteria 24 will be summarized separately by treatment group.

Clinical laboratory evaluations

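### The SAP counts only QT/QTcF exceedances by arm; the by-group summary of notable PR and QRS values promised in the protocol has no visible counterpart

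*SAP*

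**What the plan says.** **Protocol.** Under ECG, Section 12.5.1 states: "Clinically notable events such as those in Exclusion Criteria 24 will be summarized separately by treatment group". Criterion 24 (Section 5.2) sets three limits: PR above 200 msec, "QRS complex > 120 msec", and QTcF above 450 msec in men or 460 msec in women. On who reads the tracings, Section 8.4.2 says: "A central reading of standard 12-Lead ECGs will be implemented". A local reading is allowed at baseline so that eligibility can be settled. Section 11.2 has the centrally processed readings sent electronically to the sponsor. ECG parameters belong to the secondary endpoint, whose objective is a comparison with placebo (Table 2-1).

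**SAP.** In Section 7.2, ECG evaluations, a subject enters the ECG listing on the principal investigator's interpretation. The rule for each parameter is the same: "If there is any abnormality (marked as abnormal by the PI) of an ECG parameter for a subject, all measurements of this parameter" go into the listing. The numeric limits come next: "Clinically notable values will also be flagged in the listing using the following criteria", followed by the same PR, QRS and QTcF cut-offs as criterion 24. The section then plans "A categorical summary of QT/QTcF interval data based on the number of subjects meeting or exceeding predefined limits", by treatment group. No similar table is described for PR or QRS. Their absolute values are summarised by group and visit, and Section 7.3 adds boxplots by group.

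**The concern.** The SAP copies all three criterion 24 parameters into its table of notable values but carries only one of them through to a count by arm. The other two depend on a listing that opens on a judgement, although the cut-offs are written down and central numeric readings are collected.

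At stake is whether the report can say how many subjects per arm had a PR or QRS value beyond the stated limit. That is the form of comparison with placebo that Section 12.5.1 promises. The planned arms are small, 30 on LYS006 and 15 on placebo (Section 12.8.1), so one subject is 1/30 = 3.3% of one arm or 1/15 = 6.7% of the other. At that size, a count of individual subjects is more direct evidence than a by-visit mean.

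**Working it through.** The point is a comparison of texts. No stated figure has to be reproduced.

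**Step 1: the promise against the delivery.**

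| Parameter | Limit in criterion 24 | Limit repeated in SAP 7.2 | Flag inside the ECG listing | Exceedance count by arm in SAP 7.2 |
|---|---|---|---|---|
| PR | > 200 msec | yes | yes | none visible |
| QRS | > 120 msec | yes | yes | none visible |
| QTcF | > 450 msec (men), > 460 msec (women) | yes | yes | yes, from the categories above 450 or 460 |

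One of three parameters is counted by arm, which leaves 3 − 1 = 2 without a count.

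**Step 2: what opens each safety listing in SAP 7.2.**
- Vital signs: a value outside the tabulated reference range.
- Laboratory: a value outside the reference limits.
- ECG: the investigator's mark. The numeric criteria flag values already in the listing and do not bring a subject into it.

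**Step 3: trace of one value.** Take, for illustration, a centrally read post-baseline PR of 210 msec that the investigator does not mark.
- ECG listing: not triggered for PR, so the notable-value flag has nothing to attach to.
- Categorical table: not counted, because it covers QT/QTcF only.
- Adverse event tables: present only if the finding is judged clinically significant and reported as such (Protocol 8.4.2).
- Summary statistics and boxplots: the value contributes, but it is not identified or counted as beyond the limit.
- Individual plots: Protocol 12.5.1 plans overlaid plots for continuous ECG parameters. SAP 7.3 limits these to selected parameters, and the visible text does not say whether PR and QRS are among them.

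**Step 4: what cannot be sized.** The documents give no rate at which subjects cross the PR or QRS limits, and no rate at which investigators leave such values unmarked. No probability of a missed case can be derived from them.

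**The case against.** The strongest reply is that the data remain visible. PR and QRS are named safety variables (SAP 7.1), and their values feed the by-group summaries and boxplots. If the summaries include minimum and maximum, as the SAP specifies for demographic variables, a lone high PR would be that visit's maximum. Clinically significant abnormalities must be recorded as adverse events and so reach the by-arm tables. A sentence under Adverse events in SAP 7.2 also says that all safety data will be listed. All of this stands, and it limits the point. None of it gives the number of subjects per arm beyond the limit. The general listing sentence, read literally, is at odds with the specific ECG rule, and the two should be reconciled.

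A second reply is that the SAP does not displace the central reading. That is also right. Section 8.4.2 says who reads the tracings, not who decides that a value is abnormal, and nothing in SAP 7.2 swaps central values for local ones. The mismatch lies in what opens the listing and what is counted.

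A third reply is redaction. SAP Section 2, part of Other safety evaluations and the text after 7.3 are withheld. The ECG subsection shows no redaction mark, but a PR/QRS table elsewhere cannot be excluded.

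**Conclusion.** The point holds as a narrow mismatch between protocol and SAP. The by-group summary of criterion 24 events is visibly planned for QTcF and not for PR or QRS. Under the ECG listing rule, an exceedance that the investigator does not mark is not flagged. It should be corrected. It touches a descriptive secondary endpoint in a proof-of-concept trial of about 45 subjects and does not affect the primary analysis.

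Two stronger readings are tempting. A reader might infer that conduction abnormalities could vanish from the report altogether. The documents do not support that, given the other outputs through which the values or the events can appear. A reader might also infer that every later crossing is a new on-study event, because criterion 24 bars such values at entry. That does not follow. Baseline eligibility may rest on a local reading and the SAP's baseline is the last pre-dose measurement, so a central baseline value could already lie beyond the limit. A small shift near the cut-off would also count as a crossing.

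Confidence is moderate. The conclusion assumes that no redacted section already contains a by-arm PR/QRS count.

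**What to change.** In SAP 7.2, ECG evaluations:

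1. Open the listing on either the investigator's mark or any centrally read value meeting the SAP's own notable criteria, and reconcile this with the sentence under Adverse events on listing all safety data.
2. Beside the QT/QTcF categories, and over the same post-baseline window, add by-group n (%) of subjects with any PR above 200 msec and with any QRS above 120 msec, from central readings.
3. For each count, show how many of those subjects were at or below the limit at the analysis baseline, so that new crossings can be told from values already present.
4. If such a table already exists in a withheld section, cross-refer to it from the ECG subsection.

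The cost is a changed listing filter, two rows in a planned table and their split by baseline status. The cut-offs are already in the SAP and the central readings are already collected. The listing may become somewhat longer.

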### Adverse events

All AEs occurring during this clinical trial will be coded using MedDRA. All information obtained on AEs will be displayed by treatment group and subject.

Summary tables for AEs will include only AEs that started or worsened after first dose, the treatment-emergent AEs (TEAEs). However, all safety data (including those from the pre and post-treatment periods) will be listed and those collected during the pre-treatment and post-treatment period are to be flagged.

The number and percentage of subjects with TEAEs will be tabulated by system organ class (SOC) and preferred term (PT) with a breakdown by treatment and also by SOC, PT and maximum severity with a breakdown by treatment. Summaries will also be provided for the number of AEs by treatment.

Separate summaries will be provided for study medication related AEs, deaths, SAEs, and other significant AEs leading to discontinuation.

The number and percentage of subjects with events of special interest CCI will be summarized by treatment.

A subject with multiple AEs within a SOC/PT and treatment is only counted once towards the total of this SOC/PT and treatment.

Subject listings of all AEs will be provided. Deaths and other serious or clinically significant non-fatal AEs will be listed separately.

### Adverse event reporting for Clinical Trial Safety Disclosure (CTSD)

For the legal requirements of ClinicalTrials.gov and EudraCT, two required tables, 1) on TEAEs which are not SAEs with an incidence greater than X% and 2) on treatment-emergent SAEs and SAEs suspected to be related to study treatment will be provided by SOC and PT on the safety analysis set. These tables will be produced by Novartis. The value of the cutoff value X will be decided with the team when disclosure tables are prepared.

The summary will be done overall and by treatment i.e. active (LYS006) or Placebo, regardless of the dose level.

If for a same patient, several consecutive AEs (irrespective of study treatment causality, seriousness and severity) occurred with the same SOC and PT:

- a single occurrence will be counted if there is  $\leq$  1-day gap between the end date of the preceding AE and the start date of the consecutive AE
- more than one occurrence will be counted if there is  $>$  1-day gap between the end date of the preceding AE and the start date of the consecutive AE.

For occurrence, the presence of at least one SAE / SAE suspected to be related to study treatment / non-SAE has to be checked in a block e.g., among AE's in a  $\leq$  1-day gap block, if at least one SAE is occurring, then one occurrence is calculated for that SAE.

The number of deaths resulting from SAEs suspected to be related to study treatment and SAEs irrespective of study treatment relationship will be provided by SOC and PT.

### **Other safety evaluations**

Commercially Confidential Information

All other safety evaluations (e.g. pregnancy test results for women) will be listed by treatment group, subject and visit/time.

### **7.3 Graphical presentation**

Boxplots to visualize trends in longitudinal safety data (vital signs, ECG evaluations and lab parameters) will be created by treatment group. Mean and overlaying individual plots will be presented for selected parameters from vital signs, ECG evaluations and lab parameters.

Commercially Confidential Information

Commercially Confidential Information

Commercially Confidential Information

## 10 Appendix

### 10.1 Imputation rules for AE and ConMed dates

**Table 10-1 Imputation of start dates (AE, CM)**

Missing Element	Rule
day, month, and year	

• No imputation will be done for completely missing start dates

day, month	

• If available year = year of study treatment start date then

◦ If stop date contains a full date and stop date is earlier than study treatment start date then set start date = 01JanYYYY

◦ Else set start date = study treatment start date.

• If available year > year of study treatment start date then 01JanYYYY

• If available year < year of study treatment start date then 01JulYYYY

day	

• If available month and year = month and year of study treatment start date then

◦ If stop date contains a full date and stop date is earlier than study treatment start date then set start date= 01MONYYYY

◦ Else set start date = study treatment start date.

• If available month and year > month and year of study treatment start date then 01MONYYYY

If available month and year < month and year of study treatment start date then 15MONYYYY

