### 6.1.3.1 Model checking procedures

Subjects who discontinued from the study for reasons other than COVID-19 before the EoT visit, or have received rescue or prohibited medication for the treatment of UC during the treatment period will be considered failed to achieve clinical remission. Any CCI data for a subject that were recorded at or after the start of a rescue or prohibited medication should be removed from the CCI statistical analyses.

Any missing subscore will lead to a non-evaluable clinical remission status and the subject will also be considered failed to achieve clinical remission. Reasons for missing Mayo scores or subscores need to be collected to understand the impact of such analysis approach. Imputation methods such as tipping point analysis may be explored.

Discontinuation prior to EoT, or subjects for which central reading of EoT endoscopy was not available due to local COVID-19 related restrictions will be considered as missing data.

Commercially Confidential Information

The homogeneity of the total Mayo scores between subjects  
visually by each visit.

CCI  
will be explored

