**Table 10-2 Imputation of end dates (AE, CM)**

Missing Element	Rule
day, month, and year	

• No imputation will be done for completely missing end dates

day, month	

• No imputation will be done for partial end dates

day	

• No imputation will be done for partial end dates

Any AEs and ConMeds with partial/missing dates will be displayed as such in the data listings.

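### SAP Table 10-1 ignores partial stop dates, so a record with a year-only start can be imputed to begin on Day 1, after its own recorded stop month

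*SAP*

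**What the plan says.** SAP Appendix 10.1, Table 10-1, covers start dates of adverse events and concomitant medications. In the row for a missing day and month, the branch opens with "If available year = year of study treatment start date then". It then has two outcomes:

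- The start is put at 1 January of that year only under the condition "If stop date contains a full date and stop date is earlier than study treatment start date".
- In every other case the default applies: "Else set start date = study treatment start date".

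Table 10-2 says of stop dates that "No imputation will be done for partial end dates", and adds that "Any AEs and ConMeds with partial/missing dates will be displayed as such in the data listings". No rule compares an imputed start with whatever is known of the stop.

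Three parts of the SAP depend on when a record starts or whether it overlaps treatment:

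- Section 7.2, adverse events: "Summary tables for AEs will include only AEs that started or worsened after first dose".
- Section 7.2, treatment: medications before and after the start of study treatment are listed, and summarised by group.
- Section 6.1.3.1: subjects who "have received rescue or prohibited medication for the treatment of UC during the treatment period will be considered failed". A further sentence there, with the affected data redacted, removes data from the start of such a medication onwards.

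**The concern.** The month of a partial stop date is often enough to show that a record ended before Day 1. The rule discards that information and can return a start later than the recorded stop, which is impossible. Because listings show dates as collected, the imputed starts can matter only in derivations. There they would move a pre-treatment record into the on-treatment period.

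Such records are conceivable in this trial. Protocol Table 6-2 admits patients after wash-out of biologics, JAK inhibitors and immunosuppressants, and Protocol 6.2.1 asks for medications taken within the entry-criteria window to be recorded.

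**Working it through.** **1. The date rule.** The documents give no figure for it, so the check is to apply Table 10-1 literally. Day 1 = 15SEP2021 is an illustrative choice.

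| Recorded start | Recorded stop | Imputed start | Comment |
|---|---|---|---|
| 2021 | 20MAR2021 | 01JAN2021 | correct side of Day 1 |
| 2021 | MAR2021 | 15SEP2021 | after its own stop |
| 2021 | 2021 | 15SEP2021 | truly ambiguous |
| FEB2021 | MAR2021 | 15FEB2021 | correct side |
| 2020 | MAR2021 | 01JUL2020 | correct side |
| SEP2021 | SEP2021 | 15SEP2021 | truly ambiguous |

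Only the second row is wrong. The latest possible stop is 31MAR2021, and 31 March to 15 September is 168 days, about 5.5 months. The failure needs a year-only start in the Day 1 year together with a partial stop whose month is before Day 1.

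**2. How narrow this is for washed-out drugs.** Start, stop and wash-out must all fall in the Day 1 year. Biologics need at least 3 months before the screening endoscopy (Protocol Table 6-2), which is at least 4 days before baseline (Protocol 8.3.1.2). Even a stop on 1 January then requires Day 1 around 5 April or later. For the 4-week wash-out the same sum is 28 + 4 = 32 days, and for the 6-week wash-out 42 + 4 = 46 days.

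**3. The row for a missing day only.** Its default applies when the start month is the Day 1 month. A month-only stop in that month has the month's last day as its latest value, which is never before Day 1. The record is ambiguous, so this row has no such defect.

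**4. What one false failure would do, if one occurred.** Inputs from Protocol 12.4.2 and 12.8.1: 30 v 15 subjects; LYS006 prior Beta(1/3, 1/3); placebo prior a mixture of Beta(18.9, 167.4), Beta(3.2, 24.2), Beta(1.0, 3.3) and Beta(1, 1) with weights 0.43, 0.34, 0.03 and 0.2; success if Prob(diff > 0) > 90% and Prob(diff > 15%) > 50%. With x and y remitters:

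- LYS006 posterior: Beta(1/3 + x, 1/3 + 30 − x).
- Placebo posterior: components Beta(a + y, b + 15 − y), each weight multiplied by B(a + y, b + 15 − y)/B(a, b) and renormalised.
- Probability of success: the sum of Bin(x; 30, p + 0.25) × Bin(y; 15, p) over all (x, y) that meet both criteria.

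The placebo rate p is not readable in the protocol, so it is an assumption. The stated 86% at a 25-point difference is reproduced: 85.0%, 86.0%, 86.6% and 87.4% for p = 10%, 11%, 12% and 15%. With no difference and p = 12%, both criteria are met in 2.3% and neither in 91.5%, against the stated figures of below 5% and 92%.

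Forcing one LYS006 subject to failure replaces Bin(30) by Bin(29), still out of 30:

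| Assumed p | No false failure | One on LYS006 | One on placebo |
|---|---|---|---|
| 8% | 82.5% | 79.4% | 83.1% |
| 10% | 85.0% | 82.3% | 85.9% |
| 12% | 86.6% | 84.2% | 87.8% |
| 15% | 87.4% | 85.2% | 89.0% |

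At the decision boundary, 8/30 v 1/15 gives Prob(diff > 15%) = 0.586 (met) and 7/30 v 1/15 gives 0.432 (not met). This is what any single misclassified remitter would do. It is not evidence that the date rule produces one.

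**The case against.** A reader might infer that the rule turns a properly washed-out drug into a primary-endpoint failure. The documents do not support that. Section 6.1.3.1 turns on having received the drug during treatment, and nothing says the flag is built from Table 10-1 dates. A false failure would need a derivation that uses the imputed start and disregards the recorded stop month. Some SAP text is redacted, so the derivation may be specified where it cannot be read.

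Other checks would also expose an error. Protocol Table 6-2 and 6.2.3 tie prohibited or rescue use to stopping study treatment, so a false case would clash with the disposition data. Relevant deviations are determined before lock (Protocol 11.2), and eligibility and primary-variable data are fully verified (Protocol 11.3). Under Protocol 8.2 only medications from the 4 weeks before first dose need recording, so a drug stopped months earlier may not be in the data at all; Protocol 6.2.1 reaches further back.

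For adverse events the case is narrower still. They are collected prospectively from consent, within a screening period of at most 28 days, so a year-only start is unlikely.

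All of this limits the consequence. It leaves untouched the fact that the written rule returns an impossible date when the record itself holds the answer.

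**Conclusion.** The defect in the row for a missing day and month is established from the text. A year-only start in the Day 1 year with a partial stop known to precede Day 1 is imputed to Day 1. Treatment-emergent status and the prior/concomitant split would be wrong for such a record wherever they use imputed starts, taking a start on the first-dose date as on treatment.

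An effect on the primary endpoint is possible but not shown. If one LYS006 subject were falsely failed, the probability of success would drop by 2.2 to 3.1 points over assumed placebo rates of 15% down to 8%. The number of affected records cannot be estimated from the documents and may be zero. This is a small correction, worth making because the rule contradicts the data it is applied to.

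**What to change.** Before database lock:

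1. In the missing day-and-month row of Table 10-1, impute 01JanYYYY when the stop date is full and before treatment start, or is partial with its latest possible value before treatment start. The record with start 2021 and stop MAR2021 then moves from 15SEP2021 to 01JAN2021.
2. Add that no imputed start may fall after the latest possible stop date.
3. State in 6.1.3.1 that the prohibited-medication flag uses the recorded stop month and not the imputed start alone.
4. Reconcile Protocol 6.2.1 and 8.2 on how far back prior medications are recorded.

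The row for a missing day only needs no change. Ambiguous records still default to Day 1, so the rule stays conservative. The SAP cost is a short amendment and about a line of programming; the design figures do not change.
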